7.4 Interim contacts and visits

Interim visits may be performed at any time during the study, for a number of reasons, which include but may not be limited to the following:

- For administrative reasons, e.g., a participant may have questions for study staff or may need to re-schedule a follow-up visit.
- For product-related reasons, e.g., a participant may need additional tenofovir gel or want to discuss problems with adherence to gel use.
- In response to AEs. When interim contacts or visits are completed in response to participant reports of AEs, study staff will assess the reported event clinically and with laboratory and/or relevant diagnostic investigations if indicated and provide or refer the participant to appropriate medical care.
- For interim STI counseling and or treatment in response to STI symptoms.
- For interim HIV counseling and testing in response to presumed exposure to HIV or seroconversion symptoms.
- Family planning counseling and/or contraception provision.
- To provide participants with the results of confirmatory HIV test results (Appendix I).
- For other reasons at participant request.

The procedures performed at an interim visit will depend on the reasons for the visit. At the minimum, an interim visit CRF will be completed.

8. SAFETY MONITORING AND ADVERSE EVENT REPORTING

8.1 Adverse events and reporting requirements

An AE is defined as any untoward medical or social occurrence in a clinical research participant which may or may not have a causal relationship with the study product. Study product refers to tenofovir gel. New information regarding symptoms or conditions that occur during the screening period, but prior to randomization will be recorded in the participant's medical history as pre-existing conditions. All new or

worsening symptoms or conditions that occur following randomization will be considered AEs and will be recorded on the appropriate CRF.

8.2 Adverse event reporting

Study participants will be provided contact telephone numbers and instructed to contact study staff to report any AEs they may experience, except for life-threatening events for which they will be instructed to seek immediate emergency care. Depending on the severity of the event, the study staff will instruct the participant to present to their assigned study site (for mild events) or to a hospital casualty department (for serious events) for immediate evaluation. With appropriate permission of the participant, records from all non-study medical providers related to AEs will be obtained and required data elements will be recorded on study CRFs. All participants reporting an AE will be followed clinically, until the AE resolves (returns to baseline) or stabilizes. AEs that are ongoing at the time of study exit will be followed up for up to 30 days after study exit and then, if not resolved, will be referred to a health care provider for further follow-up.

Designated study staff will determine the severity of the AE and document it on the appropriate CRF. Each adverse event that the participant is aware of will be graded for severity using the most current DAIDS severity grading system.

An AE **does not** include:

- Pre-existing diseases or conditions present or detected prior to start of study product administration, which do not worsen.
- Medical or surgical procedures (e.g. surgery, endoscopy, tooth extraction, transfusion); the condition that led to the procedure is the adverse event.
- Elective hospitalization for surgery, social and/or convenience admissions or situations where an untoward medical occurrence has not occurred.

For each AE, an assessment of the relatedness to the study product will be made using the criteria and scale as outlined in the SSP manual. All AEs will be captured regardless of the association or otherwise to tenofovir gel and reported on the appropriate CRF in accordance with the SSP. All AE reports will contain at least the date the AE occurred, a brief description of the event, the relationship to study product, the action taken, the outcome, date resolved, and the seriousness of the event.

8.3 Serious adverse event (SAE) reporting

An SAE includes any experience that is fatal or life-threatening, results in persistent or significant disability/incapacity, requires or prolongs hospitalization, or is a congenital anomaly. A life-threatening AE means that the participant was, in the view of the designated study staff, at immediate risk of death from the condition as it occurred. Notification of deaths will be recorded by reflecting the medical condition that led to the death on the appropriate CRF. Reporting SAEs may require additional detailed reports and follow-up.

All serious adverse events will be reported to CONRAD, the South African MCC and the UKZN BREC.

8.4 Safety monitoring

Designated study staff will be responsible for continuous close safety monitoring of all study participants. The study statisticians will prepare routine study progress reports for review by the Protocol Team. In addition, the study statisticians will prepare routine study progress reports which include reports of AEs experienced by study participants for review by the DSMB. The membership, scope of responsibility, role and modus operandi of the DSMB will be outlined in the SSP and will include safety monitoring of enrolled participants infected with HBV. DSMB members will meet in-person and/or via teleconference regularly throughout the period of study implementation. Any deaths of study participants or other SAEs will be reviewed and final decision taken by the DSMB documented. Following its review of the data during the trial, the DSMB may recommend that the study proceed as designed, proceed with design modifications, or be discontinued. The CAPRISA 008 DSMB will conduct interim reviews of study progress (pooled across both study arms), including rates of participant accrual, retention, completion of primary and relevant secondary endpoint assessments, and clinical and laboratory adverse events including the SAE rate.

9. STATISTICAL CONSIDERATIONS

9.1 Review of study design

This is a two-arm, open-label, randomized, controlled trial among a maximum of 700 sexually active, HIV-uninfected women aged 18 years and older who previously participated in an antiretroviral (ARV) prevention study, currently utilizing or agreeing to attend family planning clinics neighboring the CAPRISA sites. A total study duration of approximately 30 months is planned, with accrual requiring approximately 12 months

9.2 Endpoints

9.2.1 Primary endpoint

Gel use is essential for the effectiveness of tenofovir gel in preventing HIV infection. The level of gel use was a strong predictor of effectiveness in the exploratory adherence analysis of the CAPRISA 004 trial. Gel use on its own and in relation to coitus were both predictors of the level of protection. Based on the CAPRISA 004 trial which demonstrated a correlation between the number of returned used applicators and the level of effectiveness against HIV infection, the primary endpoint is:

- Mean number of returned used applicators per participant per month

9.2.2 Secondary endpoints

The following secondary endpoints will be assessed:

- Clinical and laboratory adverse event and pregnancy rates
- HIV incidence rates.
- Self-reported adherence to the tenofovir gel dosing strategy (and factors influencing gel use in relation to sexual activity, condom use, and intravaginal practices)
- Self-reported service acceptability and completion rates of quarterly HIV and pregnancy testing
- HIV viral load among HIV seroconverters.
- Tenofovir resistance among HIV seroconverters.
- Vaginal cytokines.
- HSV-2 and HPV incidence rates
- Tenofovir levels (and their correlation with HIV and HSV-2 infection rates)
- Self-reported product acceptability.

9.3 Accrual, follow-up, and sample size

A maximum of 700 women (350 in each arm) will be enrolled over approximately 12 months of the total 30 month study duration. The study's DSMB will monitor key parameters that may affect the study's statistical power and sample size calculations and may therefore recommend changes to the target accrual or duration of follow-up.

The primary endpoint is gel use as assessed by the mean number of returned used applicators per participant per month. In the CAPRISA 004 trial, the mean number of returned used applicators per participant per month was 5 and the standard deviation was 3. We would like to exclude a greater than 20% (i.e., more than 1 applicator per participant per month) difference in gel use between the two study arms. A maximum sample size of 700 provides > 90% power to demonstrate whether gel use in women attending family planning services is similar to, but no more than 20% lower than gel use by women attending the CAPRISA research clinics, adjusted for 10% loss to follow-up.

9.4 Random assignment

The trial randomization plan outlines the procedures for randomization. In summary, the procedures are as follows: Enrolled participants will be assigned at random to one of the two study treatment arms in a 1:1 ratio. The randomization list used to assign individual study participants to one of the two treatment arms will be generated by a randomization statistician who is not otherwise involved in the study. This statistician will use a randomly permuted block design, stratified by site. Two or more pre-specified block sizes will be recorded on a formal randomization request form, but they will not be written in the protocol or communicated to the clinical staff in order to reduce the chance of the clinical staff anticipating the assignment of the next participant. Electronic copies of the randomization schedule and the programs used to generate the randomization schedule will be limited in access and password protected. Paper copies of the randomization schedule will be locked in a secure location at the CAPRISA office, where no unauthorized study staff will have access to them.

The randomization statistician will provide the site with sealed, opaque randomization envelopes, sequentially labeled by a PID. These envelopes will be assigned in sequential order to eligible study participants. Upon opening the envelope, the staff member will add his or her name and signature as well as the time and date the envelope was opened. Study arm allocation will be concealed until after a participant is deemed eligible to participate in the study. Once a PID is assigned, the participant will be regarded as enrolled and randomized and the randomization envelope can be opened after the PID is assigned. This is an open label trial and there will be no blinding after the envelope is opened.

9.5 Data analysis

A Statistical Analysis Plan (SAP) will outline the planned analyses. The following is a summary of the planned analyses. Any deviations to be made from this summary plan will be documented in the detailed SAP.

This is a non-inferiority study with the primary objective being to show that gel use, as measured by the mean number of returned used applicators per participant per month, in the family planning arm is not more than 20% lower than the CAPRISA clinic arm.

The analyses will be performed on an intention-to-treat (ITT) basis and on the per-protocol and as-treated populations. For the ITT analysis, participants will be analyzed according to the study arm, even if the participant did not follow the assigned procedures. The only participants excluded from this primary analysis population will be women with no post-randomization visit and no data collected. The ITT analysis could increase the chances of declaring equivalence in a non-inferiority study. We will therefore do both the ITT and the per-protocol analyses and compare the findings of both analyses. The assumption is made that the ITT and per-protocol population will give similar results. If that is not the case, the differences in the two analyses will be investigated. In a non-inferiority trial, the ITT population is not necessarily the most conservative analysis and consideration will be given to trial conduct before the decision is made to regard the ITT population as the primary population. For example, in instances with many protocol violations or low adherence to visit schedule, the per protocol analysis might be more appropriate.

The number of used applicators returned will be compared between the two treatment arms using an appropriate longitudinal method, such as generalized estimating equations or linear mixed models, adjusted for site. The null hypothesis will be that the difference between the mean in the CAPRISA arm and the mean in the family planning arm differ by more than or equal to 20%. The alternative hypothesis will be that this difference between the means is smaller than 20%. This will be a one-sided test.

The analyses of the primary and secondary objectives will be described in detail in the SAP.

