7.3 Follow-up visits

Women randomized to the intervention arm will attend monthly visits for the first 3 months of study participation. Thereafter, gel provision and monitoring will be scheduled to coincide with each participant’s

routinely scheduled family planning visits (typically every 2-3 months). Follow-up visits for women enrolled into the control arm are scheduled throughout the study follow-up period on a 28-day schedule. The visit window around a study visit is 14 days on either side. In addition to the regular follow-up requirements, additional procedures are done at study months 6, 12, 18, 24 and study exit for all participants. For participants who do not complete scheduled visits within the allowable window, the visit will be considered “missed” and relevant CRFs will be completed to document the missed visit. However, for participants who miss their month 6, 12, 18 or 24 visits, the study procedures specified to take place at these visits will be conducted at the participants’ next visit.

Participants who become pregnant during the study will be followed as usual, but gel will be withheld until they have a negative pregnancy test. For participants who become HIV infected during the study, product will be permanently discontinued once diagnosis of a HIV positive status is confirmed. HIV seroconvertors in the trial will be referred to the CAPRISA 002 Acute Infection study and/or the CAPRISA 009 treatment study for further care and follow-up. For women opting not to enroll in the CAPRISA 002 or CAPRISA 009 study they will be referred to the CAT Programme at the urban or rural site as appropriate or to other sources of care and support available to these communities.

Follow-up study visits occur monthly for the first 3 months and 2-3 monthly thereafter up to and including the study exit visit for participants in the intervention arm and monthly up to and including the study exit visit for participants in the control arm. The following study procedures will be performed during study follow-up:

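### Section 9.5 names ITT as the primary population, then reopens the choice between ITT and per-protocol on observed trial conduct, with no rule for deciding

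*Protocol*

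**What the plan says.** Protocol section 9.5 (Data analysis) lists ITT, per-protocol and as-treated analyses. It defines the ITT set and gives it primary status: "The only participants excluded from this primary analysis population will be women with no post-randomization visit and no data collected". It observes that ITT can make a non-inferiority finding easier to reach, and responds: "We will therefore do both the ITT and the per-protocol analyses and compare the findings of both analyses". It assumes that the two will agree, and adds: "If that is not the case, the differences in the two analyses will be investigated".

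The same paragraph then reopens the choice. It says that "consideration will be given to trial conduct before the decision is made to regard the ITT population as the primary population" and gives an example: "in instances with many protocol violations or low adherence to visit schedule, the per protocol analysis might be more appropriate".

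Three other parts of the protocol bear on this:

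- Section 9.4: "This is an open label trial and there will be no blinding after the envelope is opened".
- Section 7.3, control arm: "Follow-up visits for women enrolled into the control arm are scheduled throughout the study follow-up period on a 28-day schedule". For the intervention arm: "Follow-up study visits occur monthly for the first 3 months and 2-3 monthly thereafter". The same window of 14 days either side applies to both.
- Sections 3.1 and 7.3.3: used and unused applicators are collected at study visits, so the primary endpoint is observed through attendance.

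**The concern.** The section contradicts itself on which analysis decides the trial. ITT is primary in one sentence and only a candidate for primary a few sentences later. The later text sets no level of violations or non-adherence that would trigger a change, no date for the decision, and no condition that it be taken before applicator counts by arm are seen. If ITT shows non-inferiority and per-protocol does not, or the reverse, the only instruction is to investigate.

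The named trigger makes this worse. The trial tests an implementation model. The arm determines the clinic, the staff and the visit interval, and keeping women in attendance is part of what the model has to deliver. Low visit adherence may therefore be an outcome of the arm and not a flaw in conduct. A per-protocol set that excluded poor attenders would compare two groups selected after randomisation, possibly to different degrees in each arm.

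At stake are the error rate of the non-inferiority claim and the credibility of a conclusion whose deciding analysis was named late in an open-label trial.

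**Working it through.** **Inputs from the protocol (section 9.3).** Mean 5 and SD 3 used applicators per participant per month; margin 1 applicator (20%); 350 women per arm; 10% loss, leaving 315 per arm. Section 9.5 says that the test is one-sided. No alpha is stated, so 2.5% and 5% are both assumed.

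**1. The plan's own power figure.** Standard error of the difference = 3 × √(2/315) = 0.239. Margin/SE = 1/0.239 = 4.183. With zero true difference, power = Φ(4.183 − 1.960) = 98.7% at one-sided 2.5%, and Φ(4.183 − 1.645) = 99.4% at 5%. The stated figure of more than 90% holds.

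**2. Upper bound on error if the more favourable analysis is picked.** Assume that per-protocol is a random fraction f of ITT in both arms. The two test statistics then have correlation √f. At the non-inferiority boundary, the probability that at least one rejects is 1 − P(Z₁ ≤ z, Z₂ ≤ z) under a bivariate normal distribution.

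| f (assumed) | √f | Either rejects, nominal 2.5% | Either rejects, nominal 5% |
|---|---|---|---|
| 80% | 0.894 | 3.5% | 6.9% |
| 60% | 0.775 | 4.0% | 7.7% |

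If both must reject, the probability is 2 × nominal − P(either). At nominal 2.5% this is 5.0% − 3.5% = about 1.5% (f = 80%) and 5.0% − 4.0% = about 1.0% (f = 60%). A both-must-succeed rule can never exceed the error rate of ITT alone, whichever women per-protocol excludes.

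**3. How far a per-protocol set based on attendance could move the estimate.** Assume that good attenders use 5.5 applicators per month and poor attenders 3.0, in either arm. None of these inputs is in the protocol.

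- 25% poor attenders in the family planning arm, 10% in control: ITT means are 0.75 × 5.5 + 0.25 × 3.0 = 4.875 and 0.90 × 5.5 + 0.10 × 3.0 = 5.25, a deficit of 0.375. Per-protocol compares 5.5 with 5.5 and shows none.
- The same shares with the arms exchanged: ITT shows an advantage of 0.375 for family planning, and per-protocol removes that instead.

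The shift is 2.5 × (0.25 − 0.10) = 0.375 applicators either way, over a third of the margin. Its sign depends on which arm has more poor attenders.

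**4. Power if both analyses must succeed (one-sided 2.5%, zero true difference).**

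- f = 80%: 252 per arm in per-protocol, SE 0.267, per-protocol power Φ(3.742 − 1.960) = 96.3%; both succeed, 96.0%.
- f = 60%: 189 per arm, SE 0.309, per-protocol power Φ(3.240 − 1.960) = 90.0%; both succeed, 89.8%.

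The Study Schema and section 3.1 attach the power statement to stratification by study population. If that means power within each of two equal strata (157 evaluable per arm per stratum), ITT power starts at Φ(1/(3√(2/157)) − 1.960) = 84.0% at 2.5%, or 90.5% at 5%. Requiring both would lower it further.

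**The case against.** The strongest reply is that the sponsor is being careful. ITT is indeed not always conservative for non-inferiority, both analyses will be reported and compared, and the text conditions on conduct, not results. Section 4.5 standardises retention effort across arms, and section 8.4 has the DSMB review progress pooled across arms. All of this stands and limits silent selection. None of it says which analysis decides, or when.

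Three stronger readings are tempting, and the protocol does not support them.

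- *Per-protocol is defined by attendance.* It is not. Low visit adherence is given as a circumstance favouring per-protocol, not as a membership criterion. Section 12.2 lists missing or mistimed procedures as an example of a violation, which permits an inference only. The definition may properly sit in the statistical analysis plan, which is not shown.
- *The switch would favour non-inferiority.* The direction is open. After the first three months, control women have roughly two to three times as many scheduled visits, so more chances to miss one. The 0.375 example also lies inside the 1-applicator margin: it shows a distorted estimate, not a false conclusion. ITT is no perfect benchmark either, since missed visits reduce what it observes too.
- *The favourable result would be picked.* The error figures assume this, and the text does not say it. They are an upper bound under random exclusion.

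**Conclusion.** The point holds as a contradiction and an unfixed decision rule in the protocol itself. It is more than detail deferred to a statistical analysis plan: section 9.5 states that the primary population depends on observed conduct, so a later plan would have to reverse that text, not merely add to it.

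Under deliberate choice of the better result, the inflation is modest: about 1.0 to 1.5 percentage points on 2.5%, or 1.9 to 2.7 on 5%, for assumed per-protocol shares of 80% to 60%. Selection could matter more, but only if the per-protocol set excludes poor attenders, if those women use less gel, and if their share differs by arm. The protocol settles none of these conditions, so neither the size nor the direction of the bias can be claimed.

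**What to change.** In section 9.5, delete the two sentences that make the primary population depend on trial conduct, and state ITT as the primary population without qualification. State the role of per-protocol now. Preferably, non-inferiority is claimed only if ITT and per-protocol both meet the same margin. Letting ITT alone decide, with per-protocol as a pre-specified sensitivity analysis, would also control error. Either choice settles what happens when the two disagree. When the per-protocol set is defined, do not use adherence to the visit schedule as a membership criterion.

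The change is wording only, with no change to the sample size. Letting ITT alone decide costs no power. Requiring both costs the power shown above: from about 99% to about 96% with 80% retained in per-protocol, or about 90% with 60% retained, at one-sided 2.5%. It would be lower if the stated power is meant within each stratum, so the sponsor should settle that reading before choosing the rule.

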Provision of tenofovir gel and study monitoring for women enrolled in the intervention arm will be done through local family planning services where QI methodology will be used to promote reliable delivery of tenofovir gel and family planning services. Participants in the intervention arm will have monthly visits for the first three months post-enrollment; thereafter, gel provision and monitoring will be scheduled to coincide with each participant's routine family planning visit (typically every 2-3 months). Study visits in the intervention arm will be scheduled no longer than 3 months apart.

Women assigned to the control arm will have monthly scheduled visits at the CAPRISA urban or rural clinic where they will be provided with 1% tenofovir gel.

HIV and pregnancy testing will be performed at each study visit in both study arms. HIV/sexually transmitted infection (STI) risk reduction messages and condoms will be provided to all participants using consistent prevention messages. Similarly, family planning services, tenofovir gel and counseling on product adherence will be provided to all participants. Participants in both study arms will be requested to return all used and unused applicators at each study visit.

Clinical safety will be assessed pre-, during- and post-enrollment. Laboratory safety assessments will be done at enrollment, months 6, 12, 18, 24, study exit and additionally if indicated. At these visits, blood samples will be collected for urea, electrolytes, creatinine, liver function tests, full blood count, calcium and phosphate levels. Pelvic examinations, including naked eye examination of the external genitalia and speculum examination of the vagina and cervix will be conducted at enrollment, months 6, 12, 18, 24, study exit and additionally if indicated. These visits will also include collection of blood for storage of serum and plasma and genital specimens for storage to assess for markers of safety, risk exposure, product adherence, potential post-trial assessments of activity against STIs, and tenofovir resistance. For symptoms experienced between scheduled visits, the participant will be counseled to report to their assigned study site as soon as possible.

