7.2.1 Administrative, behavioral, and regulatory procedures

- Confirm eligibility
- Informed consent for enrollment and stored specimens
- Update locator information
- HIV/STI risk reduction counseling and provision of condoms
- Randomization and participant identification (PID) number allocation
- Baseline data collection including sexual behavior
- Family planning counseling
- Product adherence counseling

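### The primary model sentence has no term for time covered, although the arms return applicators over different intervals; if gel use wanes, equal weighting of returns favours non-inferiority

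*Protocol*

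**What the plan says.** The primary endpoint in section 9.2.1 is "Mean number of returned used applicators per participant per month". Section 9.5 puts the non-inferiority objective on the same scale: "as measured by the mean number of returned used applicators per participant per month, in the family planning arm is not more than 20% lower", with the research-clinic arm as comparator. Section 9.3 sets the margin at one applicator per woman per month, 20% of a mean of 5 with SD 3.

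The sentence in 9.5 that describes the comparison is shorter: "The number of used applicators returned will be compared between the two treatment arms using an appropriate longitudinal method". It offers GEE and mixed models as examples, and site is the only adjustment. It names no offset, no weighting for interval length and no definition of a month.

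The two arms run on different clocks. In section 7.3, "Follow-up visits for women enrolled into the control arm are scheduled throughout the study follow-up period on a 28-day schedule". In section 3.1, "Participants in the intervention arm will have monthly visits for the first three months post-enrollment"; after that, visits coincide with routine family planning visits, typically two to three months apart. Sections 3.1 and 7.3.3 have used applicators collected at each study visit in both arms.

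**The concern.** A longitudinal model needs repeated records, and in this protocol the records arise at visits. After month 3, a family planning record covers two to three months and a control record covers 28 days. A model that does not know how much time each record covers cannot treat them alike.

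Restating each return as a monthly rate puts the arms on one scale but does not fix the weighting. The three early monthly visits are a much larger share of the family planning records than of the control records. If women use more gel early on, the family planning average leans towards that period and the control average does not. The difference comes from the schedule, not from behaviour. It raises the family planning mean, which is the anti-conservative direction when the aim is to show that this arm is not much lower.

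**Working it through.** **The plan's own figure.** Inputs from 9.3: SD 3, margin 1, 350 per arm, 10% loss, so 315 per arm. Standard error = 3 × √(2/315) = 0.239, and 1/0.239 = 4.18. Power = Φ(4.18 − 1.96) = 98.7% at one-sided 2.5%, or Φ(4.18 − 1.645) = 99.4% at one-sided 5%. The stated power above 90% is met. Mean, SD and margin are already per month, so nothing below changes the sample size.

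**Assumptions.** Follow-up is 24 months, within the 18 to 30 months implied by section 3.1. Nominal months are equal in both arms, so that only the weighting is tested. Control has 24 monthly returns. Family planning returns are either 3-monthly (months 1, 2, 3, 6, …, 24: 10 returns) or 2-monthly (months 1, 2, 3, 5, …, 23, then 24: 14 returns). The first three months supply 3/24 = 12.5% of control returns, but 3/10 = 30% or 3/14 = 21% of family planning returns. The waning curves are assumed and identical in both arms.

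**Overstatement of the family planning mean, with each return as a monthly rate and equal weight per return.**

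- Step, 7 per month to month 3 and then 5. True mean (3×7 + 21×5)/24 = 5.25. 3-monthly: (3×7 + 7×5)/10 = 5.60, overstated by 0.35. 2-monthly: (3×7 + 11×5)/14 = 5.43, overstated by 0.18.
- Linear, 7 − t/8, from 7 to 4. True mean 7 − 12/8 = 5.50. 3-monthly: interval midpoints sum to 99, mean 9.9, rate 7 − 9.9/8 = 5.76, overstated by 0.26. 2-monthly: midpoints sum to 158, mean 11.29, rate 5.59, overstated by 0.09.
- Flat use: no overstatement on either schedule.

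The control mean equals the true mean in every case, because its returns are evenly spaced.

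**False non-inferiority at a true ratio of 0.80.** Let d be the overstatement. The test quantity (family planning mean − 0.8 × control mean) should centre on zero, but centres on 0.8d. Take SD 3 in control and 0.8 × 3 = 2.4 in family planning. The standard error is then √[(2.4² + 0.8² × 3²)/315] = √(11.52/315) = 0.191, and the false-positive rate is Φ(0.8d/0.191 − 1.96).

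| Curve | Visits | d | 0.8d/0.191 | False non-inferiority |
|---|---|---|---|---|
| Step | 3-monthly | 0.35 | 1.46 | 31% |
| Linear | 3-monthly | 0.26 | 1.10 | 19% |
| Step | 2-monthly | 0.18 | 0.75 | 11% |
| Linear | 2-monthly | 0.09 | 0.37 | 6% |
| Flat | either | 0 | 0 | 2.5% |

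Simulation with gamma-Poisson counts, 315 per arm, 4,000 runs and 3-monthly visits, including exponential declines from 7 to 4, gave 16-31% under waning and about 2.5% under flat use. Total count over total time gave 2.1-2.9% on the same curves. At one-sided 5%, the equally weighted analysis gave 26-41%.

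**The case against.** The strongest reply is that the protocol never says counts are compared by visit. Endpoint, objective and margin are all per woman per month. Section 9.5 is a summary, offers its models as examples and leaves detail to the SAP, which is not at hand. A count model with a time offset would already fit its wording. All of this stands. What remains is that the one sentence describing the comparison omits the time scale that the endpoint needs, and that the per-month label does not settle the weighting.

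The reply also notes that the size depends on assumptions: how much use wanes, equal weight per return, no time term, and how many women attend 2-monthly. This stands too. A linear time term removes the bias under linear waning, but leaves about 0.21 under the step with 3-monthly visits. Section 9.5 names no such term. Evidence for waning is indirect: section 1.3 reports protection falling from 50% at 12 months to 39% by 30 months or exit, and section 9.2.1 ties protection to gel use.

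Three stronger readings are tempting and should not be drawn:

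- *Raw counts per visit are compared.* At 5 per month over 24 months this would set about 12.0 (3-monthly family planning) against 4.6 (control), and non-inferiority would be almost automatic. It contradicts the stated endpoint.
- *A month is 28 days in control and a calendar month in family planning.* That would shift the comparison by 30.4375/28 = 1.087, so a true 5 versus 4 would show as 5 versus 4.35. The protocol does not define a month, but nowhere gives the arms different ones.
- *Late family planning returns are lost.* Section 7.3 says "The visit window around a study visit is 14 days on either side" and calls later visits missed. But section 6.3.3 requires all returned applicators to be reconciled and logged, and nothing excludes late returns from the endpoint.

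The second and third need a clarifying clause and no more.

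**Conclusion.** The concern holds as a gap in the stated method. The comparison sentence in 9.5 has no time-covered term while the return intervals differ by arm, and converting to monthly rates does not by itself remove the resulting bias. Under the assumed declines over 24 months, the family planning mean is overstated by about 0.1-0.35 applicators per month. False non-inferiority at a true 20% deficit is about 6-11% with 2-monthly visits and 16-31% with 3-monthly visits.

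These figures assume a one-sided 2.5% level (the protocol gives sidedness but no level), 315 analysed per arm, equal weight per return and no time term. With flat use the bias is zero. A reader should not conclude that the trial will falsely declare non-inferiority; the protocol leaves room for an analysis that would avoid it and should commit to that analysis.

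**What to change.** In section 9.5, state that returned used applicators are analysed as a rate over the actual days covered. Either use each woman's total count over her total days, or fit a log-link count model with a log-days offset and robust variance by participant. If visit-level records are kept, an independence working correlation makes the estimate total count over total days. Use one month length for both arms, and count every applicator returned at any attendance, inside or outside the visit window.

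Keep the adjustment for site. As an optional gain in precision, add baseline coital frequency if the enrolment item "Baseline data collection including sexual behavior" (section 7.2.1) captures it. Leaving it out is not an error.

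The cost is a few lines in 9.5 and the matching SAP programming. Counts and accountability records are already kept under sections 6.3.3 and 7.3.3, so no new data, visits or participants are needed.
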